## **2.6 Analysis supporting secondary efficacy objectives**

The FAS will be used for all below efficacy analyses.

### **2.6.1 Secondary endpoint(s).**

#### **2.6.1.1 Secondary efficacy endpoints for core part**

The secondary efficacy endpoints for core part are listed as follows:

- Absolute change in LDL-C from baseline at Day 150
- Percentage and absolute change in PCSK9, TC, HDL-C, non-HDL-C, ApoB, ApoA-1, Lp(a) and TG from baseline at Day 150

All secondary efficacy endpoints for core part will be analyzed using the same ANCOVA model as for the primary efficacy endpoint. Lp(a) will be log-transformed before modeling. The model will include treatment as fixed effect, and baseline value as a covariate. The adjusted mean difference between inclisiran and placebo and corresponding two-sided 95% CIs will be provided separately. Nominal two-sided p-values will also be provided.

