9.4.1.1 Efficacy and/or pharmacodynamic endpoints for core part

The secondary efficacy endpoints for core part are listed as follows:

- Absolute change in LDL-C from baseline at Day 150
- Percentage and absolute change in PCSK9, TC, HDL-C, non-HDL-C, ApoB, ApoA-1, Lp(a) and TG from baseline at Day 150

All secondary efficacy endpoints for core part will be analyzed using the same ANCOVA model as for the primary efficacy endpoint. Lipoprotein (a) will be log-transformed before modeling. The model will include treatment as fixed effect, and baseline value as a covariate. The adjusted mean difference between inclisiran and placebo and corresponding two-sided 95% CIs will be provided separately.

Details of the analyses for secondary efficacy endpoints for core part and sensitivity analyses if necessary will be specified in the SAP.

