#### **Post-baseline assessment**

Post-baseline assessments are defined as those assessments that were collected after the first dose of study treatment.

When change from baseline is of interest the following formula will be used for each scheduled visit and time-point where baseline and post-baseline values are both available:

**Absolute change from baseline** = post-baseline value – baseline value.

**Percentage change from baseline** = (absolute change from baseline / baseline value)\*100.

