## 2.6.3 Handling of intercurrent events

### 2.6.3.1 Estimands for core part

The same methods as specified in [Section 2.5.3](#) will be applied to all secondary efficacy endpoints for core part. Multiple imputation will be conducted for log-transformed Lp(a) values. The details are specified in [Appendix 5.4.2](#).

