2. Missing data will be imputed under MAR assumption in this step. The same imputation model as specified for control-based PMM will be used except that the missing data will be multiply imputed using data within each treatment group. SAS PROC MI will be utilized using the FCS REG statement, where only previous measurements will be included for each imputed variable. A total of 100 datasets (out\_step2) will be created. These fully imputed datasets will be utilized in step 3.

3. For participants handled by intercurrent events of treatment discontinuation, if the measurement is missing in (out\_step1) and after treatment discontinuation, set this value back to missing (out\_step3). These datasets (out\_step3) will be utilized in step 4.
4. If there are enough RDO data, the RDO based imputation model will be used in this step. SAS PROC MI will be utilized using the FCS REG statement, where previous measurements and an indicator of on- or off-treatment status at the same visit with the response will be included for each imputed variable. This imputation will be implemented based on data within each group. If there are not enough RDO data, the control-based PMM will be used in this step. With this imputation model, the missing value in the inclisiran group will not be constructed from the observed data in the inclisiran group but rather from the observed and imputed data in the control group. SAS PROC MI will be utilized using the FCS REG statement, where only previous measurements will be included for each imputed variable. The MNAR statement in SAS PROC MI will also be used under MNAR assumption for inclisiran group. After this step, the 100 datasets(out\_step4) will be fully imputed. These datasets will be utilized in step 5. (Which model will be used in this step will be determined before Core Part database lock)
5. For participants who died, set the values after death using his/hers baseline value. (out\_step5)
6. Datasets (out\_step5) will be used in this step. The absolute change and the percentage change values will be calculated in each of the imputed datasets.
7. These 100 datasets will be analyzed using the ANCOVA model for the LDL-C endpoints.
8. The results from the 100 datasets will be combined using Rubin's method via SAS PROC MIANALYZE procedure.

#### 5.4.1.2 Supplementary analysis under estimand 1

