## 5.4.2 Analysis supporting secondary objective(s)

### Objectives for core part

The same imputation models and procedure as specified in [Appendix 5.4.1.1](#) will be applied to all secondary efficacy endpoints for core part. For Lp(a), log-transformation will be taken before the imputation and the imputation model will exclude variables at Day 30 and Day 90 visits.

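### Does logging Lp(a) before imputation and modelling, with no stated back-transformation, leave its percentage and absolute change endpoints undefined?

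*SAP*

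**What the plan says.** Percentage and absolute change in Lp(a) at Day 150 are both core-part secondary endpoints (Protocol 3.2.1; SAP 2.6.1.1). They take the ANCOVA used for the primary endpoint. On the model, SAP 2.6.1.1 states "Lp(a) will be log-transformed before modeling" and "The model will include treatment as fixed effect, and baseline value as a covariate"; Protocol 9.4.1.1 has the same instruction, "Lipoprotein (a) will be log-transformed before modeling". The reported contrast is an adjusted mean difference with a 95% CI.

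On imputation, SAP 2.6.3.1 states "Multiple imputation will be conducted for log-transformed Lp(a) values" (2.6.4.1 repeats it). SAP 5.4.2 adds "For Lp(a), log-transformation will be taken before the imputation and the imputation model will exclude variables at Day 30 and Day 90 visits" and otherwise applies the procedure of 5.4.1.1. Step 6 of that procedure reads "The absolute change and the percentage change values will be calculated in each of the imputed datasets", and step 7 reads "These 100 datasets will be analyzed using the ANCOVA model for the LDL-C endpoints". SAP 2.1.1 defines absolute change as post-baseline minus baseline, and percentage change as 100 times "absolute change from baseline / baseline value".

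**The concern.** Values enter the imputation as logs, and the changes are derived afterwards, yet no sentence returns the values to concentration units. The modelling sentence is also awkward. The primary ANCOVA has the change as its response, and a fall is a negative number, which has no logarithm. So the log must apply to something else, and the text does not say whether that is the Day 150 value, the baseline covariate or both.

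Three readings are conceivable:

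1. Apply the SAP 2.1.1 formulas directly to logged values.
2. Model the log ratio and report a ratio of geometric means. This yields no absolute change in concentration units.
3. Exponentiate, derive both changes on the original scale, and compare means.

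If two programmers chose differently, two declared endpoints would carry different quantities under the same label. Absolute change is the more exposed, because a log-scale response does not deliver it.

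**Working it through.** The plan states no Lp(a) figure to reproduce. The check is textual first, then illustrative.

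**Which reading the text supports**

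- SAP 2.5.2: the ANCOVA response is the change from baseline.
- SAP 2.6.1.1: the same model applies, and the contrast is a mean difference, not a ratio.
- SAP 1.2.2.1 and Protocol 3.2.1: the core secondary estimands keep the primary summary measure, a difference of means.
- SAP 2.1.1: both changes are defined from the values, with no exception for Lp(a).
- SAP 5.4.1.1, step 6: the changes are derived after imputation.

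These agree with reading 3. The log in SAP 2.6.3.1, 2.6.4.1 and 5.4.2 then serves to keep a skewed variable well behaved in the imputation regression. Reading 2 conflicts with the mean-difference contrast and the shared summary measure.

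**Why reading 1 would not survive programming**

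For a proportional fall f from baseline b it gives 100 × ln(1 − f) / ln(b). With f = 0.25:

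| Baseline b | Result |
|---|---|
| 10 | 100 × (−0.288) / 2.303 = −12.5 |
| 20 | 100 × (−0.288) / 2.996 = −9.6 |
| 100 | 100 × (−0.288) / 4.605 = −6.2 |

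The same true fall gives three answers, so the result changes with the unit. A 20% fall from 0.8 to 0.64 gives +100, with the sign reversed. An analyst would see at once that this is not a percentage change.

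**How far the sensible readings differ**

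All inputs here are assumed: 100 per group; lognormal baseline with median 20 and log-SD 1.0; SD of the within-person log change w = 0.25; f = 0.25; 2,000 simulated trials; no missing data. The table gives the median estimate and the central 95% of trials.

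| Analysis | Percentage | Absolute (units) |
|---|---|---|
| Original scale, log baseline covariate | −25.7 (−32.2 to −19.5) | −8.35 (−12.31 to −5.07) |
| Original scale, unlogged baseline covariate | −25.7 (−32.0 to −19.6) | −8.21 (−11.82 to −5.14) |
| Log-ratio ANCOVA, exponentiated | −24.9 (−29.8 to −19.8) | none |

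The covariate scale hardly matters. Varying one input at a time (median 10 to 40, log-SD 0.7 to 1.2, w 0.15 to 0.35, f 0.15 to 0.35), the two original-scale versions differ by at most 0.06 points for percentage change and 0.36 units for absolute change.

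The gap between the arithmetic and geometric results has a simple form. Under these assumptions the difference in mean percentage change is −100f × exp(w²/2), and the geometric result is −100f, so the gap is 100f × (exp(w²/2) − 1).

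- Base case: 25 × (exp(0.03125) − 1) = 0.8 points, as in the table (25.7 − 24.9).
- w = 0.15: 25 × (exp(0.01125) − 1) = 0.3.
- w = 0.35: 25 × (exp(0.06125) − 1) = 1.6 (the simulated range over all scenarios was 0.3 to 1.4).
- w = 0.6, f = 0.20: 20 × (exp(0.18) − 1) = 3.9.

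The base-case sampling range of the percentage estimate is 32.2 − 19.5 = 12.7 points.

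**Two side issues**

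The log base has no effect after exponentiation. It matters only if a raw log difference is reported (−0.288 natural, −0.125 base 10, for a 25% fall). The LDL-C wording of step 7 is not specific to Lp(a): SAP 5.4.2 extends the procedure to every core secondary endpoint.

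**The case for a change.** The best case for a change is that the gap is real and cheap to close. SAP 2.6.3.1 and 2.6.4.1 send the reader to Appendix 5.4.2 for the details, and that appendix is silent on the return to the original scale. The SAP leaves some items to separate programming specifications, but not this one. Log-ratio ANCOVA is a familiar way to analyse a skewed marker, so a programmer could adopt it in good faith. The result would be a geometric-mean ratio under a mean-difference heading, with no absolute change, while SAP section 4 records no departure from the protocol.

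Part of this stands. The modelling sentence fits poorly with the rest of the text, and the small gap between readings is not general: it grows with within-person variability, to about 4 points at a log-SD of 0.6. It does not follow that the endpoints are undefined. Absolute change is declared by name and defined by formula, so an analyst who kept a log response would find an endpoint missing and return to the original scale. Choosing between an arithmetic and a geometric summary for percentage change is a preference, and the plan's summary measure already favours the arithmetic one. There may also be little left to pre-specify: Amendment 2 is timed before the final lock, whereas Amendment 1 was timed before the core-part lock, so the core-part results may already exist.

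**Conclusion.** No change to the plan. This is missing detail that a competent analyst fills in one way: exponentiate the imputed Lp(a) values, derive both changes by the SAP 2.1.1 formulas, and report mean differences as the estimand requires. The logging sentence then does no harm, whether taken to mean the imputation model or the baseline covariate.

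The reach is small. Lp(a) is one of nine secondary lipid and PCSK9 markers. Its p-values are nominal (SAP 2.6.1.1), there is no multiplicity claim (SAP 2.6.2), power was not assessed for secondary endpoints (Protocol 9.9.2), and Lp(a) is not among the secondary markers given subgroup analyses (SAP 2.6.6). The primary LDL-C analysis is untouched. The sensible readings of percentage change differ by 0.3 to 1.6 points for within-person log-SDs of 0.15 to 0.35 at a 25% fall, and by about 4 points at 0.6 with a 20% fall. Every Lp(a) input is an assumption, since the documents give no unit, distribution or expected effect. The conclusion rests mainly on how the sections fit together, and less on those figures.

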#### **2.6.1.2 Secondary efficacy endpoints for extension part**

The secondary efficacy endpoints for extension part are listed as follows:

- Percentage change in LDL-C from baseline at Day 330 for inclisiran group
- Absolute change in LDL-C from baseline at Day 330 for inclisiran group

The secondary efficacy endpoints for extension part will be analyzed descriptively. Mean percentage and absolute change from baseline at Day 330 in inclisiran group will be provided, respectively, as well as the 95% confidence intervals.

## 2.6.2 Statistical hypothesis, model, and method of analysis

No multiple comparisons including primary and secondary efficacy endpoints will be made.

## 2.6.3 Handling of intercurrent events

### 2.6.3.1 Estimands for core part

The same methods as specified in [Section 2.5.3](#) will be applied to all secondary efficacy endpoints for core part. Multiple imputation will be conducted for log-transformed Lp(a) values. The details are specified in [Appendix 5.4.2](#).

### 2.6.3.2 Estimands for extension part

The secondary efficacy analysis for extension part will account for different intercurrent events as explained in the following:

- **Discontinuation of study treatment:** Retrieved drop out (RDO) data collected after discontinuation from study treatment will be used for the analysis (treatment policy). Missing data after discontinuation from study treatment will be multiply imputed based on RDO data, and when there are no sufficient RDO data, a control-based PMM (using the Core Part data) will be used for multiple imputation. The detailed information is specified in [Appendix 5.4.2](#).
- **Use of prohibited LLT:** Use of prohibited LLT (PCSK9 monoclonal antibodies taken before Day 330 visit assessment or other LLT taken within 30 days before Day 330 visit assessment) will be treated in a hypothetical scenario of what would happen had those LLT not been taken, and those participants behaved like other participants in the same treatment group (hypothetical strategy). Data after those intercurrent events will be excluded for the analysis and will be multiply imputed under MAR assumption.
- **Death:** Death due to CV or non-CV causes is considered as an unfavorable outcome (composite strategy). The LDL-C values at Day 330 after death will be set using the participant's baseline values.

In the case of multiple intercurrent events, death will be the dominant one in the analysis (if present). If a participant experiences only two other intercurrent events and usage of prohibited LLT occurs first, s/he will be handled by the event of usage of LLT (hypothetical strategy). If treatment discontinuation occurs prior to usage of prohibited LLT, then data after usage of LLT will be set missing and s/he will be handled by the event of treatment discontinuation (treatment policy). The detailed imputation model and algorithm are specified in [Appendix 5.4.2](#). Number and percentage of participants by each intercurrent event will be summarized by treatment group in final analyses. Listing will also be provided.

## 2.6.4 Handling of missing values not related to intercurrent event

### 2.6.4.1 Estimands for core part

The same methods as specified in [Section 2.5.4](#) will be applied to all secondary efficacy endpoints for core part. Multiple imputation will be conducted for log-transformed Lp(a) values. The details are specified in [Appendix 5.4.2](#).

### 2.6.4.2 Estimands for extension part

Missing values not related to intercurrent event will be multiply imputed under MAR assumption. The detailed imputation model and algorithm are specified in [Appendix 5.4.2](#). The secondary efficacy analysis for extension part will be conducted on each multiply imputed dataset, and the results from each of those imputed datasets will be combined using Rubin's rule.

## 2.6.5 Sensitivity analyses

The same sensitivity analysis as specified in [Section 2.5.5](#) will be conducted for LDL-C endpoint at Day 150.

## 2.6.6 Supplementary analyses

The same subgroup analyses as specified in [Section 2.5.6](#) will be performed for absolute change in LDL-C at Day 150 and percentage change in PCSK9, TC, non-HDL-C and ApoB at Day 150. The difference in the adjusted means between treatment groups, corresponding two-sided 95% CI and two-sided p-value will be provided for each of the subgroups. The adjusted means in both treatment groups, corresponding two-sided 95% CI will also be provided for each of the subgroups.

A plot displaying descriptive mean percentage change in LDL-C from baseline up to Day 360 visit for both treatment groups will be provided, using the observed data.

## 2.7 Safety analyses

For all safety analyses, the SAF will be used, unless otherwise specified. All listings and tables will be presented by treatment group. Baseline data will be summarized where appropriate (for change from baseline summaries).

### 2.7.1 Adverse events (AEs)

An AE will be counted as a treatment emergent AE (TEAE) if the AE started after the first dose of study treatment or the AE present prior to start of study treatment but increased in severity based on preferred term. Since the investigators are required to enter any worsened AE as a separate record, implementation-wise an AE is a TEAE as long as its start date is on or after date of first dose of study treatment. All TEAEs will be classified into core part TEAEs and extension part TEAEs.

- The core part TEAEs will be defined as TEAEs with the start date on or prior to the switching date.

- The extension TEAEs will be defined as TEAEs with the start date after the switching date.

Overall summary of TEAE will be displayed by treatment group and study part. The number (and percentage) of participants with TEAEs will be summarized:

- By study part, treatment group, primary system organ class (SOC) and preferred term (PT).
- By study part, treatment group, SOC, PT and maximum severity.
- By study part, treatment group, PT.
- By study part, treatment group, SOC and PT for TEAEs leading to study drug discontinuation.
- By study part, treatment group, SOC and PT for TEAEs related to study drug.

The number (and percentage) of participants with treatment emergent serious adverse events (TESAE) will be summarized:

- By study part, treatment group, SOC and PT.
- By study part, treatment group, SOC and PT for TESAEs related to study drug.

In core part analyses, the number (and percentage) of participants with TESAE will also be summarized for overall study:

- By treatment group, SOC and PT.
- By treatment group, SOC and PT for TESAEs related to study drug.

Unless otherwise specified, SOCs will be sorted alphabetically and, within each SOC, the PTs will be sorted in descending order of frequency. If a participant reported more than one adverse event with the same PT, the AE will be counted only once. A participant with multiple adverse events within a SOC is only counted once towards the total of the SOC. In case of summary by severity or relationship to study drug, summary will be done using the most severe or related occurrence respectively. Listing of all AEs and SAEs will be provided in both core part analyses and final analyses, regardless of whether they are treatment emergent.

The number of deaths resulting from SAEs suspected to be related to study treatment and SAEs irrespective of study treatment relationship will be provided by study part, treatment group, SOC and PT.

For above by-part summary tables, OLS will be used for extension part data in final analyses. Besides, above summary tables for overall study will also be provided using SAF in final analyses. Subgroup analyses for safety will be performed in subgroups as specified in [Section 2.2.1](#). Overall summary of TEAE by subgroup will be provided by treatment group in core part analyses. Subgroup analyses of all treatment emergent adverse events (TEAE) will also be displayed by treatment group, SOC and PT in core part analyses. The number (and percentage) of participants with TEAEs will be provided for each category of subgroup.

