### **AE reporting for CT.gov**

For the legal requirements of clinicaltrials.gov, two required tables on treatment emergent adverse events which are not serious adverse events with an incidence greater than X% (X will

be selected prior to final database lock)\* and on treatment emergent serious adverse events and SAE suspected to be related to study treatment will be provided by SOC and PT on the safety set population.

If for a same patient, several consecutive AEs (irrespective of study treatment causality, seriousness, and severity) occurred with the same SOC and PT:

- a single occurrence will be counted if there is  $\leq$  1 day gap between the end date of the preceding AE and the start date of the consecutive AE
- more than one occurrence will be counted if there is  $>$  1 day gap between the end date of the preceding AE and the start date of the consecutive AE

For occurrence, the presence of at least one SAE / SAE suspected to be related to study treatment / non SAE has to be checked in a block e.g., among AE's in a  $\leq$  1 day gap block, if at least one SAE is occurring, then one occurrence is calculated for that SAE.

The number of deaths resulting from SAEs suspected to be related to study treatment and SAEs irrespective of study treatment relationship will be provided by SOC and PT.

These summaries will be provided only after full study completion.

\*Note: the X% has been chosen as 5% before the final database lock.

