### **2.7.1.1 Adverse events of special interest / grouping of AEs**

The number and percentage of participants with adverse event of special interest (AESI) will be summarized for each topic for:

- TEAE by study part, treatment group and PT

In final analyses, OLS will be used for the summary tables of extension part data. Besides, summary tables for overall study will also be provided using SAF. In core part analyses, summary of TEAE by treatment group, PT and maximum severity and of TESAE by treatment group and PT will also be provided. PTs will be sorted in descending order of frequency in the total column. If a participant reported more than one adverse event with the same PT, the AE will be counted only once. If a participant reported more than one AE within the same AESI, the participant will be counted only once at that AESI.

Adverse event of special interest will include the following:

- Hepatotoxicity
- Injection site reaction

For injection site reaction, separate listing will be provided for participants with injection site reaction AE in both core part analyses and final analyses. The time to the first injection site reaction TEAE will also be summarized by treatment group and study part using the following categories: No ISR,  $\leq$ 4h,  $>$ 4h to  $\leq$ 12h,  $>$ 12h. The time (hours) to the event will be calculated from the most recent administration of study drug. The duration of the first injection site reaction TEAE will also be summarized by treatment group and study part using the following categories: No ISR,  $\leq$ 4h,  $>$ 4h to  $\leq$ 7 days,  $>$ 7 days to  $\leq$ 14 days,  $>$ 14 days. Total number of TEAE at the injection site per participants will be summarized in categories (e.g. 1, 2, 3, and  $>$ 3 etc.)

by treatment group and study part. In final analyses, OLS will be used for the summary tables of extension part data. Besides, all summary tables of injection site reaction will also be provided for overall study using SAF.

Case Retrieval Strategy (CRS) will be used to determine the MedDRA search criteria to be used to identify the AESI. The CRS listing will be provided.

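### An injection-site reaction that worsens becomes two records under the SAP, so the events-per-participant table counts it twice and, if the first record is closed at that point, its tabulated duration is too short

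*SAP*

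**What the plan says.** SAP 2.7.1 (Adverse events) explains why a start date is enough to identify a treatment-emergent event: "Since the investigators are required to enter any worsened AE as a separate record", and so "implementation-wise an AE is a TEAE as long as its start date is on or after date of first dose of study treatment".

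SAP 2.7.1.1 makes injection site reaction one of two adverse events of special interest and plans three dedicated summaries by treatment group and study part:

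- Onset: "The time to the first injection site reaction TEAE will also be summarized by treatment group and study part".
- Duration: "The duration of the first injection site reaction TEAE will also be summarized by treatment group and study part". The categories are no reaction, up to 4 hours, over 4 hours to 7 days, over 7 to 14 days, and over 14 days.
- Number: "Total number of TEAE at the injection site per participants will be summarized in categories", with 1, 2, 3 and more than 3 given as examples.

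The same section has two count-once sentences: "If a participant reported more than one adverse event with the same PT, the AE will be counted only once" and "If a participant reported more than one AE within the same AESI, the participant will be counted only once at that AESI".

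The SAP has a joining rule in one place only, under AE reporting for CT.gov. It opens "If for a same patient, several consecutive AEs (irrespective of study treatment causality, seriousness, and severity) occurred with the same SOC and PT" and counts a single occurrence when at most 1 day separates the end of one record from the start of the next. Those tables are produced only after the full study is complete.

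**The concern.** The number and duration tables are meant to describe reactions, but they are built from records, and the SAP says that a worsening creates a new record. A mild reaction that becomes moderate after one injection therefore enters the number table as two events, while the registry tables would count the same data as one.

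This matters because injection-site events are the only drug-related adverse reaction that protocol section 2.3 identifies for inclisiran. That section and section 2.2 report a higher incidence than on placebo, so any distortion should fall mainly on the inclisiran group. If duration is also cut at the point of worsening, the table understates exactly the reactions that got worse.

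**Working it through.** The plan states no figure to reproduce. The check applies the SAP's wording to example records, then applies the registry joining rule to the same records.

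**Inputs**
- Record rule and treatment-emergent rule: SAP 2.7.1.
- Number table and duration categories: SAP 2.7.1.1.
- Joining rule: AE reporting for CT.gov, gap = start of next record − end of preceding record, joined if at most 1 day.
- Duration = end − start. For a joined reaction, latest end − first start.

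| Records of one participant (study days) | Count as written | First duration as written | Count joined | Duration joined |
|---|---|---|---|---|
| 1–5, worsened 5–17 | 2 | 5 − 1 = 4 days (over 4 h to 7 days) | 1 | 17 − 1 = 16 days (over 14 days) |
| 1–5, worsened 5–10 | 2 | 4 days (over 4 h to 7 days) | 1 | 10 − 1 = 9 days (over 7 to 14 days) |
| 1–3, worsened 3–5 | 2 | 3 − 1 = 2 days (over 4 h to 7 days) | 1 | 5 − 1 = 4 days (same category) |
| 1–17 left open, worsened 5–17 | 2 | 17 − 1 = 16 days (over 14 days) | 1 | 16 days (same category) |
| 1–3 and 90–92, two separate reactions | 2 | 2 days (over 4 h to 7 days) | 2 | 2 days (same category) |

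**Reading the table**
- The double count appears in every row with a worsening, whether or not the first record is closed.
- The shortened duration appears only when the first record is closed. It changes the category in two of those three examples.
- Joining leaves a true repeat reaction after the next injection as two.

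**What is not affected.** Incidence by preferred term or by topic counts a participant once. Maximum severity takes the worst record. Time to first reaction uses the start of the first record, which a later record does not move.

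**Size.** Neither the reaction rate p nor the worsening rate w is in the documents. Assume p from 2% to 20%, w from 5% to 20%, and 100 participants per arm (protocol, Treatment Groups).
- Expected number affected = 100 × p × w. Lowest: 100 × 0.02 × 0.05 = 0.1. Middle: 100 × 0.10 × 0.10 = 1. Highest: 100 × 0.20 × 0.20 = 4.
- Chance of at least one = 1 − (1 − p × w)^100. Lowest: 1 − 0.999^100 = 0.095. Middle: 1 − 0.99^100 = 0.634. Highest: 1 − 0.96^100 = 0.983.

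**The case against.** **The recording clause is about something else.** It follows the case of an event present before treatment that then increases in severity, and an injection-site reaction cannot precede the first injection. Protocol 8.6.1 describes following a detected event to resolution, with changes in severity assessed at each visit. Part of this stands: the form-completion instructions are not in the documents. But the clause speaks of any worsened event without limiting it to pre-existing ones, so the double count follows from the text as it is.

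**The same-preferred-term sentence already prevents it.** Protocol 2.3 lists five injection-site terms, so a count of distinct terms could fill the categories 1, 2, 3 and more than 3. That reading is possible, but it would also erase genuine repeat reactions of the same kind after later injections. The topic-level sentence counts participants and would put everyone affected at 1. Neither sentence addresses duration. Both fit the incidence tables.

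**The number table is openly a count of events, and a listing is provided.** True. The separate injection-site listing at both analyses lets a reader trace linked records, which limits the harm.

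**Stepwise records may be rare.** This stands. Protocol 2.3 describes these reactions as mild, sometimes moderate, and transient. The next scheduled visit comes about 30 days after the Day 1 and Day 180 injections and 60 days after those on Day 90 and Day 270, so a brief reaction may be reported afterwards as one event.

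**Stronger readings to resist.** A reader might infer that durations are certainly cut short. The documents nowhere say that the first record is closed at worsening. The end-to-start wording of the registry rule suggests it but does not establish it. A reader might also quote a percentage inflation of the count. With one extra record per worsening reaction, that percentage is just the assumed worsening rate restated.

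**Conclusion.** The point holds as a gap in specification with a minor effect. On the SAP's wording, the number table counts a reaction that worsens once as two. The duration table is wrong only for a participant's first reaction, only if that reaction worsens, and only if its first record is closed then. Even so, the broad categories absorb some of the error.

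Under the assumed rates, 0.1 to 4 participants per arm are affected, and the protocol's description of these reactions points to the lower part of that range. Both tables are descriptive and carry no test. The primary analysis, incidence, maximum severity and time to first reaction do not change. The one boundary case is a reaction that straddles the switching date, whose records would fall in different study parts. The correction is a cheap improvement that makes the two tables describe reactions and agree with the registry counts.

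**What to change.** In SAP 2.7.1.1, for the number and duration tables only:

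1. Join consecutive injection-site records of the same participant and preferred term when the gap is at most 1 day, as in the ClinicalTrials.gov rule. Treat overlapping records as joined.
2. Run the joined occurrence from the first start to the latest end, and give it the maximum severity of its records.
3. Assign it to the study part of its first start date. SAP 2.7.1 allocates each record by its own start date, so a reaction that begins on the switching date and worsens afterwards would otherwise appear in both parts.
4. State whether a worsening coded to a different injection-site preferred term is joined. Joining by term alone would miss it, and would leave two concurrent terms after one injection as two events.

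The cost is a few sentences and some added programming. The registry rule is specified only for tables produced after full study completion and does not derive a duration. The documents do not show that it has been programmed, and the injection-site tables are also needed for the core part.
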